There were six reported serious adverse events during the treatment phase of the study. Four study-related serious adverse events were reported: two incidents of decreased VA consequent to adverse events of vitreous hemorrhage, one incident of endophthalmitis, and one incident of decreased VA consequent to the incident of endophthalmitis. Two non-study-related serious adverse events were reported: gastric adenocarcinoma and rotavirus infection. The two incidents of vitreous hemorrhage were likely caused by post-operative bleeding and were determined to be related to the Implant insertion procedure. The single incident of endophthalmitis was observed at the 2-week post-Implant insertion visit and was considered possibly related to the Implant insertion procedure. The duration of this event was 14 days.

Of the 76 study-related adverse events, 7 were ongoing at the time of study exit. These ongoing events were vitreous haze (3), and single incidents of vitreous hemorrhage, VA decrease, foreign body sensation in the eye, and retinal pigment epithelium tear.

Thirteen patients entered the 24-month safety-monitoring phase (one patient was lost to follow-up after the 12-month follow-up); out of 13 patients, 12 completed the safety-monitoring phase and 1 was lost to follow-up after 21 months. There were a total of eight reported adverse events during the safety-monitoring phase of the study. Four adverse events were considered related (possibly, probably, or definitely) to the Implant insertion procedure, the refill procedure, or drug treatment. These related adverse events were cataract progression (3) and a single incident of mild ocular discomfort. Two additional incidents of cataract progression, one incident of blurred vision, and one incident of leg edema were not considered study-related by the investigator. No serious adverse events were reported during the safety-monitoring phase.

There were no patient deaths during the 12-month treatment phase (the status of the 2 patients lost to follow-up during the 24-month extended follow-up phase was not able to be confirmed), no adverse events led to patient withdrawal or dose reduction, and no adverse events represented a previously unsuspected important adverse effect of the device (implantation procedure or Implant).

Refer to the RPDS IB for further details.

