### **Concurrent Ocular Conditions**

- BCVA using ETDRS charts lower than 20/200 Snellen equivalent in the fellow eye
- Retinal pigment epithelial tear involving the macula in the study eye
- Any concurrent intraocular condition in the study eye (e.g., cataract, glaucoma, or diabetic retinopathy) that, in the opinion of the investigator, would either: require surgical intervention during the study to prevent or treat visual loss that might result from that condition or affect interpretation of study results
- Active intraocular inflammation (grade trace or above) in the study eye
- History of vitreous hemorrhage in the study eye within 3 months prior to the randomization visit
- History of rhegmatogenous retinal detachment or macular hole (Stage 3 or 4) in the study eye
- History of idiopathic or autoimmune-associated uveitis in either eye
- Active infectious conjunctivitis, keratitis, scleritis, or endophthalmitis in either eye
- Aphakia or absence of the posterior capsule in the study eye
  - Previous violation of the posterior capsule break in the study eye is also excluded unless it occurred as a result of yttrium aluminium garnet laser posterior capsulotomy in association with prior, posterior chamber intraocular lens implantation.
- Spherical equivalent of the refractive error in the study eye demonstrating more than 8 diopters of myopia
- For patients who have undergone prior refractive or cataract surgery in the study eye, the preoperative refractive error in the study eye does not exceed 8 diopters of myopia

- Intraocular surgery (including cataract surgery) in the study eye within 3 months preceding the randomization visit
- Uncontrolled ocular hypertension or glaucoma in the study eye (defined as intraocular pressure [IOP] > 25 mmHg or a Cup to Disc ratio  $\geq 0.8$ , despite treatment with anti-glaucoma medication) and any such condition for which the investigator feels may require a glaucoma filtering surgery while in the study
- History of glaucoma-filtering surgery, tube shunts, or microinvasive glaucoma surgery in the study eye
- History of corneal transplant in the study eye

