#### **4.1.2 Safety Population**

The safety population will be composed of all patients who received at least one study treatment. Patients will be summarized by treatment arm and analyzed according to the treatment actually received and not according to the treatment they were randomized to receive, in the event of a discrepancy. This population will be used for safety summaries and analyses.

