### **4.6 SAFETY ANALYSES**

The safety analyses will use the safety population as described in Section 4.1 and 4.1.2. Missing data will not be imputed.

Adverse events (AEs) are coded using the current MedDRA version. Rates will be provided for intravitreal patients and PDS patients by dose arm and pooled across PDS arms.

For safety analyses, unless otherwise specified, AEs after the start of study treatment (intravitreal injection or Implant) will be included in the analyses; AEs from patients who are explanted will be included up to a follow-up period of 90 days after explant; the post-explant ocular AEs considered related to PDS will also be included in the analyses regardless of the timing of the AE onset. To fully characterize these patients' safety, a listing will be provided for ocular AEs that occurred  $\geq 90$  days after explant.

Frequency tables including patient incidence rates will be provided for the following:

- Ocular AEs and SAEs (study and fellow eye)
- Non-ocular AEs and SAEs (study and fellow eye)
- Adverse events of special interest (study and fellow eye)
  - AEs resulting from medication errors
  - An AE considered to be sight threatening
  - Suspected transmission of an infectious agent by the study drug
  - AEs resulting from use error or from intentional misuse of the PDS
  - ADEs, that is, AEs that are considered to be related to the PDS and to the use of the PDS
- Adverse events potentially related to the PDS Implant or Implant procedures:
  - Vitreous hemorrhage
  - Endophthalmitis
  - Retinal detachment
  - Conjunctival retraction
  - Conjunctival erosion
  - Conjunctival bleb
  - Conjunctival filtering bleb leak
  - Hyphema
  - Cataract

For AEs potentially related to the PDS Implant or Implant procedures in the study eye, incidence tables will be generated using the following time windows relative to first dose or implant surgery:

- $\leq 1$  month (up to the end of Month 1 visit window, 37 days)
- $> 1$  month
- during the entire study

In addition, ocular AEs and SAEs will be provided by causality as determined by the investigator.

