Adverse events (AEs) potentially related to the PDS Implant or Implant procedures will be summarized separately for two subgroups of patients based on the IFU version in use at the time of their randomization (before IFU 10 vs. IFU 10 forward). There was a study pause to evaluate post-implantation vitreous hemorrhage and modifications were made beginning with Version 10 with the aim to reduce the risk of vitreous hemorrhages.

Non-ocular AEs and SAEs will be tabulated using the following time windows relative to first ranibizumab injection or device implant following randomization:

- Cumulative rates through 10-month follow-up for each patient
- Cumulative rates for through the end of the study (expected Month 38)

A listing of patients who died during the study will be provided.

The number and percentage of patients with positive serum anti-drug antibodies (ADA) at baseline and post-baseline during the study period will be tabulated. Impact of positive serum ADA on efficacy and safety will be explored. A listing of patients with positive serum antibodies to ranibizumab will be provided.

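### The planned cataract rate counts pseudophakic study eyes that are not at risk, so the absolute rate and the absolute Implant-ITV difference are understated; add a rate among eyes phakic at baseline

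*SAP*

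**What the plan says.** **Measure and event list.** SAP 4.6 states "Frequency tables including patient incidence rates will be provided for the following". Under "Adverse events potentially related to the PDS Implant or Implant procedures" it lists nine events, the last being Cataract. For the study eye, these events are tabulated up to the end of the Month 1 window, after it, and over the entire study.

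**Denominator.** SAP 4.6 also states "The safety analyses will use the safety population as described in Section 4.1 and 4.1.2", and SAP 4.1.2 defines that set: "The safety population will be composed of all patients who received at least one study treatment". SAP 4.1 removes the site with serious GCP non-compliance from the main safety tables. No condition on lens status applies.

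**Display.** "Rates will be provided for intravitreal patients and PDS patients by dose arm and pooled across PDS arms". The only further split of the implant-related events is by surgical instructions: they "will be summarized separately for two subgroups of patients based on the IFU version in use at the time of their randomization".

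**Eligibility.** Protocol 4.1.2 (Concurrent Ocular Conditions) excludes aphakia but not pseudophakia. It excludes prior breach of the posterior capsule, except laser capsulotomy "in association with prior, posterior chamber intraocular lens implantation". It sets a preoperative myopia limit for eyes with earlier cataract surgery, and bars cataract surgery only in the 3 months before randomization.

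**Lens status elsewhere.** It is not a stratification factor (SAP 3.1) and is not named in the baseline comparability summary (SAP 4.3).

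**The concern.** A study eye with an artificial lens adds to the denominator of the cataract rate but can never add to its numerator. The planned percentage therefore answers how often cataract was reported per treated patient. It does not give the risk for a patient who still has a natural lens, which is the figure a phakic candidate for an intraocular implant needs. Because lens status is neither tabulated nor used as a subgroup, a reader could not recover that risk from the planned output.

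The event deserves a usable rate. Protocol 1.3 reports, from the Phase I study of 20 patients, one traumatic cataract related to insertion. In the later monitoring phase of 13 patients it reports three incidents of cataract progression considered related. It then adds "Two additional incidents of cataract progression", which the investigator did not consider study-related. Traumatic cataract is also one of the prespecified device-associated events in Protocol 6.5.1.

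**Working it through.** The documents state no expected cataract rate and no pseudophakic share, so there is no planned figure to reproduce.

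**Inputs**
- Planned arm sizes: 60 per Implant arm (180 pooled) and 40 ITV (protocol synopsis).
- Pseudophakic share q: not in the documents; assumed 20% to 60%.
- Cataract risk r in phakic eyes: not in the documents; 10% is used as an example, and 10% v 5% for the difference.

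**1. Absolute rate.** Only the phakic fraction can have an event, so tabulated rate = (1 - q) x r. For pooled Implant patients with r = 10%:

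| q | phakic eyes | expected events | tabulated rate | rate in phakic eyes |
|---|---|---|---|---|
| 20% | 144 | 14.4 | 8.0% | 10% |
| 40% | 108 | 10.8 | 6.0% | 10% |
| 60% | 72 | 7.2 | 4.0% | 10% |

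The ratio of tabulated to phakic rate, 80% down to 40%, does not depend on r.

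**2. Absolute difference.** With equal q in both groups, tabulated difference = (1 - q)(r_Implant - r_ITV). A true 10% v 5%, a difference of 5 points, is shown as 4, 3 or 2 points at q = 20%, 40% or 60%.

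**3. Risk ratio.** With equal q, (1 - q) cancels: 10%/5% = 2.0 at every q. Balanced lens status does not bias the ratio.

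**4. Precision.** With zero events in n eyes, the one-sided 95% upper bound is 1 - 0.05^(1/n). For n = 60 it is 4.9%. At q = 40% an arm of 60 has 36 phakic eyes, and the bound is 8.0%.

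**5. How much chance imbalance in lens status matters.** Take r = 10% in both groups, so p = (1 - q)r. The large-sample variance of the log ratio is:
- all treated: [(1 - p)/p] x (1/40 + 1/180);
- phakic only: [(1 - r)/r] x (1/40 + 1/180)/(1 - q).

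The gap between them, [q/(1 - q)] x (1/40 + 1/180), is the part due to random lens status. The 95% factor is exp(1.96 x square root of the variance).

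| q | expected ITV events | variance, all treated | variance, phakic | 95% factor, all treated | 95% factor, phakic | part due to lens status |
|---|---|---|---|---|---|---|
| 20% | 3.2 | 0.351 | 0.344 | x/÷ 3.2 | x/÷ 3.2 | 2% |
| 40% | 2.4 | 0.479 | 0.458 | x/÷ 3.9 | x/÷ 3.8 | 4% |
| 60% | 1.6 | 0.733 | 0.688 | x/÷ 5.4 | x/÷ 5.1 | 6% |

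Changing the denominator barely narrows the between-arm ratio. With so few ITV events these large-sample factors are only approximate.

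**The case against.** The case for leaving the table alone is that all-treated patient incidence is the usual descriptive safety measure, the study is exploratory, no decision rule uses the cataract percentage, and a phakic rate could be produced later. It is true that the planned table is not an error in itself. That does not make its percentage a risk for eyes that can develop cataract.

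Two stronger readings are tempting and should not be drawn.
- *That lens imbalance could create or hide an Implant-ITV difference.* Lens status is not stratified, and the pseudophakic shares of 180 and 40 patients could differ by about 14 to 17 points by chance (95% range). But with only about 2 to 3 ITV events expected in the example, this supplies about 2% to 6% of the variance of the log ratio. Sampling error dominates with either denominator.
- *That Phase I showed five implant-related cataract progressions.* Two of the five were judged unrelated. The text counts incidents rather than patients and does not name the eye. Phase I was also open-label at one site, with a different Implant body material and release control element. It supports interest in the event and gives no rate.

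Two further reservations stand. The size depends on an assumed q. And cataract surgery during the study is permitted (Protocol 4.5.1), so eyes also leave the risk set later, which a baseline flag does not capture.

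**Conclusion.** The point holds for the absolute rate, the absolute Implant-ITV difference and the apparent precision. The planned cataract percentage is (1 - q) times the phakic rate: 80% down to 40% of it for an assumed q of 20% to 60%. The structure follows directly from SAP 4.6, SAP 4.1.2 and Protocol 4.1.2. The size cannot be fixed from the documents, which give neither the pseudophakic share nor a cataract rate. The point does not extend to the between-arm ratio, which is unbiased under balanced lens status and would be estimated little better with a phakic denominator. This is a worthwhile, inexpensive improvement to a descriptive safety table; it affects no primary or secondary efficacy conclusion.

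**What to change.** In SAP 4.6, for Cataract (and traumatic cataract where shown), add study-eye incidence among eyes phakic at baseline, by arm and pooled across Implant arms, with the number phakic in each. Keep the all-treated line beside it. In SAP 4.3, add baseline lens status to the comparability table.

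Derive lens status from the surgical history already collected (Protocol 4.6.1). Check it against the slit-lamp record or the screening lens photograph where these record it; the documents do not confirm that they do, since the slit-lamp grading scales cited cover only flare/cells and vitreous hemorrhage, and images may simply be stored.

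The cost is a short SAP addition and one derived baseline flag, with no new assessment. The stated rate will look less favourable and rest on fewer eyes. A footnote should say that cataract surgery during the study is not accounted for.

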## **6.5 SAFETY ANALYSES**

All patients receiving at least one study treatment will be included in the safety analysis.

Counts and incidence rates by treatment group for the following safety endpoints will be provided:

- Ocular and non-ocular adverse events and serious adverse events
- "Prespecified RPDS-associated adverse events" (see Section 6.5.1)
- Positive serum antibodies to ranibizumab

For "prespecified RPDS-associated adverse events", the incidence in all implant arms patients will also be summarized.

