### **6.5.1 Adverse Events**

Verbatim descriptions of treatment-emergent adverse events will be mapped to thesaurus terms. Treatment-emergent adverse events will be defined as events beginning during or after surgical insertion/explantation of the Implant or the first ranibizumab ITV injection through the completion of the study or until a patient discontinues prematurely. Adverse events will be tabulated by body system, high-level term, and preferred term. Separate summaries will be prepared for non-ocular and ocular adverse events, with events in the study eye and fellow eye summarized separately. Serious adverse events will be summarized similarly. Adverse events leading to discontinuation from the study or treatment will be listed and tabulated.

ADEs are adverse events that are considered to be related to the RPDS and to the use of the RPDS. Of particular interest are the following "Prespecified RPDS-associated adverse events":

- Vitreous hemorrhage associated with a >30-letter decrease of BCVA on ETDRS chart compared with the last assessment of BCVA prior to the onset of vitreous hemorrhage lasting > 1 month
- Reduced VA (> 30 letters loss from previous scheduled visit)
- Traumatic cataract
- Endophthalmitis
- Damage to sclera
- Retinal detachment
- Interference of the Implant with visual field

In addition to the "Prespecified RPDS-associated adverse events", any other ocular adverse events and serious adverse events attributed by the investigator to the:

1) Implant insertion procedure, 2) Implant refill procedure, 3) Implant explantation procedure, and 4) study drug, will be reported.

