#### **7.5 PASS/FAIL CRITERIA TO BE APPLIED TO THE RESULTS OF THE DEVICE CLINICAL INVESTIGATION**

The RPDS clinical investigation will be considered to successfully demonstrate Implant functionality if the following objective is met:

- Establish that there is no evidence that the initial Implant clogging rate within 9 months exceed 10%

The RPDS clinical investigation will be considered to successfully demonstrate RPDS safety if the following objective is met:

- Demonstrate that the AE profile observed when ranibizumab is administered using the Implant is clinically acceptable as compared with ranibizumab dosed using conventional ITV injection. In other words, any complications associated with Implant insertion, refill, or explantation, or associated with the long term presence of the Implant within the posterior chamber of the eye, are manageable and are acceptable in an overall benefit-risk assessment versus ITV dosing.

This will include a characterization of the “Prespecified RPDS-associated AEs”, that is, those ADEs that have been pre-specified as being most relevant for the risk assessment of the Implant and the procedures of insertion, refill, and explantation.

For each AE (including “Prespecified RPDS-associated AEs”) observed during the clinical study, the CRF will collect a separate assessment of investigator causality for each “study intervention” element, that is, investigator causality for “study drug” (i.e., ranibizumab [for both Implant arms and ITV dosing arm]), investigator causality for “procedures” (for both Implant arms and ITV dosing arm), and investigator causality for each of the RPDS components (for Implant arms only – the Implant, the Initial Fill Needle, the Insertion Tool, the Refill Needle, and the Explant Tool). Investigators will be trained on the requirement to assess each AE for potential causal association to “drug”, “procedure” and each of the “RPDS” device components —so that they may determine whether there is a causal association with one, more than one, or none of the “Study intervention” elements.

If these objectives are not met, further design changes will be mandated.

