The analyses specified in this document supersede the analysis plan described in the Study GX28228 Protocol, Version 8. Additional supportive analyses were added in this amendment to provide further evaluation of the treatment benefits.

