### **2.2.3 Safety Outcome Measures**

The safety outcome measures are as follows:

- Incidence of adverse events of special interest (AESIs): Adverse events (AEs) associated with ranibizumab, the Implant, Implant-associated procedures, and/or ancillary devices
- Incidence of “pre-specified PDS-associated AEs”
- Incidence of ocular and non-ocular AEs and serious adverse events (SAEs)
- Incidence of positive serum antibodies to ranibizumab

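### The SAP keeps the prespecified device-associated adverse events as a safety outcome but neither defines nor tabulates the set; its nine-term list matches only two of the seven events as defined

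*SAP*

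**What the plan says.** Protocol section 6.5.1 names seven prespecified events, and protocol Appendix 21 (the device plan) repeats them in sections 4.2, 5.4 and 14.7. Some are defined narrowly. The hemorrhage item begins "Vitreous hemorrhage associated with a >30-letter decrease of BCVA on ETDRS chart" and adds a condition of more than 1 month. The acuity item is "Reduced VA (> 30 letters loss from previous scheduled visit". The cataract item is "Traumatic cataract".

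Protocol section 6.5 asks for counts and incidence rates of these events by treatment group and adds that "the incidence in all implant arms patients will also be summarized". Appendix 21 section 5.4 plans an end-of-study comparison of their incidence between implant and intravitreal patients. Appendix 21 section 7.5 includes a characterisation of them in the safety judgement and describes them as "those ADEs that have been pre-specified as being most relevant for the risk assessment of the Implant".

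SAP section 2.2.3 retains the incidence of "pre-specified PDS-associated AEs" as one of four safety outcomes. SAP section 1 states: "The analyses specified in this document supersede the analysis plan described in the Study GX28228 Protocol, Version 8"; section 2.1 says much the same. The table that SAP section 4.6 plans nearest to this outcome is headed "Adverse events potentially related to the PDS Implant or Implant procedures" and has nine terms. The same list drives the time-window tables and the tables that compare patients before and from version 10 of the surgical instructions (IFU 10).

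**The concern.** The SAP names an outcome and then gives no definition of it and no table for it. The list that seems to stand in its place has a different name and different content. Because the SAP governs, a programmer who follows it would produce no incidence for the set that protocol section 6.5 and Appendix 21 call for.

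The narrow definitions matter most for hemorrhage. SAP section 4.6 reports that the study was paused to evaluate hemorrhage after implantation and that the surgical instructions were changed. As planned, the comparison around IFU 10 counts hemorrhage of any severity and does not isolate the severe, persistent form that the protocol singled out. Appendix 21 section 7.5 also says that design changes follow if its objectives are not met, so the events it relies on should be reported as defined.

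**Working it through.** No sample size or power figure bears on this point. The check sets the two lists side by side: the seven events of protocol section 6.5.1 against the nine terms of SAP section 4.6.

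| Protocol 6.5.1 | Nearest term in the SAP 4.6 list | Status |
|---|---|---|
| Vitreous hemorrhage with >30-letter BCVA loss, >1 month | Vitreous hemorrhage | Broader: both conditions gone |
| Reduced VA, >30 letters | None | Absent |
| Traumatic cataract | Cataract | Broader: cause dropped |
| Endophthalmitis | Endophthalmitis | Same |
| Scleral damage | None | Absent |
| Retinal detachment | Retinal detachment | Same |
| Implant interference with visual field | None | Absent |

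Count: 2 same + 2 broader + 3 absent = 7. Not tabulated as defined: 2 + 3 = 5 of 7. In the other direction, 9 − 4 = 5 SAP terms have no prespecified counterpart: four conjunctival terms (retraction, erosion, bleb, filtering bleb leak) and hyphema.

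The next step is whether another planned SAP output fills the gap.

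- **General ocular adverse event tables, and adverse device effects among the events of special interest (SAP 4.6).** These would show scleral damage, traumatic cataract or field interference if reported, but not as a set and without the severity or duration conditions.
- **Sight-threatening events of special interest (SAP 4.6).** This is the nearest table for large acuity loss. Protocol section 5.2.3 defines the category differently: a loss of at least 30 letters lasting more than 1 hour, with a differently worded reference assessment, or any of several alternatives (surgical intervention, severe inflammation, investigator opinion). The prespecified item is strictly more than 30 letters, against the previous scheduled visit, with no duration condition.
- **BCVA loss summaries (SAP 4.4.2.1).** The thresholds go no further than 15 letters, loss is measured from baseline, and patients rescued or explanted before Month 9 are censored.
- **Ocular assessments (SAP 4.6.4).** Hemorrhage is tabulated by slit-lamp grade, with no link to letters lost or duration. Visual field testing is not among the assessments listed.

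None of these applies the prespecified definitions, and none gives an incidence for the set.

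**The case against.** The strongest reply is that little is hidden. Two events are tabulated as defined. Two sit inside broader terms that contain them. The other three, if reported, fall within the general ocular, device-effect or sight-threatening tables, and ocular events are also summarised by causality. The safety analysis is descriptive in a Phase II study, and Appendix 21 section 7.5 sets a qualitative test of clinical acceptability with no threshold on these events. Protocol section 6.5 and Appendix 21 still call for the set, so the defect is a mismatch between documents.

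Most of this stands, and it rules out the reading that the safety objective would have no result at all. It also rules out treating the SAP list as wholly different, since four of its nine terms overlap. It does not remove the gap: the outcome in SAP section 2.2.3 has no matching analysis, and the mismatch bites because the SAP declares that it prevails.

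A reader might also infer that the nine-term list was chosen after the two interim analyses. The current SAP does postdate both, but earlier SAP versions are not available, so the date the list first appeared cannot be established. The interims are described as efficacy analyses, and the amendment rationale speaks only of added safety analyses, not of a replacement. The documents do not support the inference.

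Finally, a table derived purely from BCVA data would change the definition, because protocol section 6.5.1 presents these as adverse events. That objection is right and shapes the fix.

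**Conclusion.** The concern holds as a gap between a retained outcome and the planned analysis. Two of seven prespecified events are tabulated as defined, two in broader form, and three are not on the list. The SAP as written yields no incidence for the set by arm or pooled over implant arms. This rests on reading the SAP as the governing analysis document, as it says of itself, and on taking the definitions in protocol section 6.5.1, because the SAP supplies none. The events are not invisible and the primary efficacy analysis is untouched. It should be corrected before the safety tables are produced.

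**What to change.** Add to SAP section 4.6 an incidence table of the seven events as defined in protocol section 6.5.1, by dose arm, pooled over implant arms, and for the intravitreal arm. Mark field interference as not applicable for intravitreal patients: they have no implant, and under protocol section 4.6.5 field testing is done only in implant patients at equipped sites.

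Base the table on reported adverse events. Use recorded BCVA to apply the condition of more than 30 letters to the hemorrhage and acuity items, and the condition of more than 1 month to the hemorrhage item only. The derivation rules should settle two details:

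- Whether the duration refers to the hemorrhage or to the letter loss, since the protocol's wording allows either.
- Which visits count as scheduled for the acuity item, since protocol Appendix 1 has BCVA tested on Days 2, 7 and 14 in the implant arms and Appendix 2 has no such visits in the intravitreal arm.

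Keep the nine-term list, with its time-window and IFU 10 tables, as additional analyses. If the sponsor instead intends the nine terms to replace the outcome, the SAP should say so and justify it, and SAP section 2.2.3 and Appendix 21 sections 5.4 and 7.5 should be aligned.

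The cost is one more table and a short set of derivation rules, using data already collected.

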### **Length of Study**

The estimated study duration is 38 months.

Patients randomized to the Implant treatment arms will have the Implant (pre-filled with ranibizumab) surgically inserted in the study eye at their Day 1 visit, after which they will be evaluated monthly for the need for an Implant refill, based upon protocol-specified refill criteria, until the Sponsor decides, based on the primary analysis results, to either terminate the study and discontinue study treatment, or offer patients entry into the RPDS *Extension Study*. The duration of their participation in the study is expected to last approximately 13–38 months dependent on the date of their randomization to the study.

Patients randomized to the ITV injection treatment arm (control) will be treated monthly with ITV injections of ranibizumab *until the Sponsor decides, based on the primary analysis results, to either terminate the study and discontinue study treatment, or offer patients entry into the RPDS Extension Study*. The duration of their participation in the study is expected to last approximately 13–38 months dependent on the date of their randomization to the study.

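### SAP 4.6 splits Implant-related adverse events by IFU version with no stated window, and beyond 37 days crude incidence is not comparable because the earlier patients are followed longer

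*SAP*

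**What the plan says.** SAP 4.6 lists a family of events linked to the Implant or its procedures: vitreous hemorrhage, endophthalmitis, retinal detachment, conjunctival retraction and erosion, two kinds of bleb event, hyphema and cataract. The measure is patient incidence: "Frequency tables including patient incidence rates will be provided for the following". For this family in the study eye, "incidence tables will be generated using the following time windows relative to first dose or implant surgery". The windows are up to 1 month ("up to the end of Month 1 visit window, 37 days"), more than 1 month, and "during the entire study".

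The next paragraph says the same family will be "summarized separately for two subgroups of patients based on the IFU version in use at the time of their randomization". It explains that enrolment paused to look into vitreous hemorrhage after implantation, and that IFU 10 was meant to lower that risk. It does not say which windows apply to the split.

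The Protocol Synopsis (Length of Study) expects participation of "approximately 13–38 months dependent on the date of their randomization to the study". For non-ocular events only, SAP 4.6 adds an equal-length window: "Cumulative rates through 10-month follow-up for each patient".

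**The concern.** IFU version at randomization is a calendar split, and follow-up in this trial is also set by calendar date, because everyone stops at about the same time. At equal retention, each patient randomized before IFU 10 is observed longer than each patient randomized after it. Crude incidence over an open-ended window rises with time observed. An event with the same underlying risk in both groups will therefore appear less often after IFU 10.

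No time-to-event estimate or equal-length window beyond 37 days is planned for this split. SAP 4.6.1 summarises exposure by treatment arm, not by IFU subgroup, so a reader could not adjust from the planned tables. The events most exposed are those that continue to appear: cataract, conjunctival erosion or retraction, and late endophthalmitis. The Device Clinical Investigation Plan (section 7.5) judges safety partly on complications of the Implant's long-term presence. An apparent improvement after IFU 10 that came only from shorter observation could mislead that judgement.

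**Working it through.** **Inputs from the documents.** Enrolment about 24 months (Protocol 3.1). Primary analysis data about 4 months after the last patient's Month 9 visit (Protocol 3.2). Participation 13–38 months (Synopsis). Early window 37 days (SAP 4.6).

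**Reproducing the stated range.** Last patient: 9 + 4 = 13 months. First patient: 24 + 9 + 4 = 37 months, against the stated 38, which is given as approximate. The early window is 30 + 7 = 37 days.

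**Assumptions.** The documents do not date IFU 10, so I put the switch at month 6, 12 or 18 of enrolment. Accrual is uniform, nobody drops out, and the hazard λ is constant and identical before and after, so there is no true IFU effect.

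**Follow-up.** With the study ending at month 37 and a switch at month c, mean follow-up is 37 − c/2 before and 37 − (c + 24)/2 after. The gap is 12 months for any c.

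**Entire-study incidence.** If follow-up is uniform between a and b months, mean crude incidence is

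1 − [exp(−λa) − exp(−λb)] / [λ(b − a)].

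Take a 12-month risk of 10%, so λ = −ln(0.9)/12 = 0.00878 per month, and a switch at month 12:

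- Before IFU 10 (a = 25, b = 37): 1 − (0.8029 − 0.7226)/0.1054 = 23.8%.
- IFU 10 onward (a = 13, b = 25): 1 − (0.8921 − 0.8029)/0.1054 = 15.3%.
- After/before ratio: 0.64.

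| Switch (month) | Mean follow-up, before v after (months) | Entire study, before v after | Ratio | More than 1 month, before v after | Ratio |
|---|---|---|---|---|---|
| 6 | 34 v 22 | 25.8% v 17.5% | 0.68 | 25.0% v 16.6% | 0.66 |
| 12 | 31 v 19 | 23.8% v 15.3% | 0.64 | 23.0% v 14.4% | 0.63 |
| 18 | 28 v 16 | 21.7% v 13.1% | 0.60 | 20.9% v 12.2% | 0.58 |

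Over 12-month risks of 5–20% the entire-study ratio is 0.59–0.71, so incidence is 1/0.71 = 1.4 to 1.0/0.59 = 1.7 times higher before IFU 10. If data are cut at the last patient's Month 9 visit (month 33), the ratio is 0.51–0.66, or about 1.5 to 1.95 times higher before.

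**Equal windows.** At the 10% risk, incidence to 37 days is 1.06% in both groups. To 9 months it is 7.6% in both, and to 10 months 1 − 0.9^(10/12) = 8.4% in both. The artefact disappears.

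**A mainly perioperative event.** Assume 10–50% of patients have the event within 37 days, with 2% per year thereafter. With 10% early and a switch at month 12, entire-study incidence is 14.4% v 12.7%, a ratio of 0.88. Over all cases, at either cutoff, the ratio is about 0.87–0.98.

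**Would rates per patient-year over the whole study solve it?** Not for front-loaded events. In that same case, patients with an event per 100 patient-years are 14.4/(31/12) = 5.6 before and 12.7/(19/12) = 8.0 after, so IFU 10 looks 1.4 times worse with no true difference. With 50% early and a switch at month 18, the figures are 52.2/(28/12) = 22.4 and 51.2/(16/12) = 38.4, or 1.7 times worse.

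**The case against.** A reader might infer that the SAP has chosen whole-follow-up incidence as the IFU comparison. The text does not say so. The split follows directly after the three windows for the same events, and the natural reading is that the tables are repeated by subgroup. One of them, to 37 days, has equal follow-up. This objection stands. It does not rescue the later results, however. If the windows carry over, two of the three are open-ended. If they do not, the section's default rule counts events from the start of treatment with no common end. On neither reading is there an equal-follow-up result beyond 37 days.

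A reader might also infer that IFU 10 would look safer for vitreous hemorrhage even if it changed nothing. The documents do not support that as a material effect. The SAP describes the target as hemorrhage after implantation; the 37-day window captures early events fairly, and the entire-study distortion for such an event is small.

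Two further points have weight. The tables are descriptive, with no test or decision rule attached to the split. The size also rests on assumptions: a pause in enrolment would change the 12-month gap, and dropout and the truncation of most events at 90 days after explant are not modelled. These limit how firmly the ratios can be stated. They do not alter the direction when retention and hazard are equal, and a two-column table by IFU version will be read as a comparison.

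**Conclusion.** The point holds in a limited form. The SAP does not state the window for the IFU-version summary, and it plans no equal-follow-up measure after 37 days. The 37-day comparison is sound. The later-window and entire-study comparisons are not, and for accruing events they favour IFU 10: crude incidence is about 1.4 to 1.7 times higher before IFU 10 at study end with no true effect. That size depends on uniform 24-month accrual, constant hazard, no dropout, a switch at month 6 to 18 and a 12-month risk of 5–20%. For mainly perioperative events, on the assumed early and late risks, the entire-study after/before ratio stays at about 0.87–0.98. The primary endpoint is unaffected.

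**What to change.** In SAP 4.6:

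- State that the comparison by IFU version uses the 37-day window, and that this is the main comparison for vitreous hemorrhage.
- For later events, compare over a common per-patient window through Month 10, as the section already does for non-ocular events, or give Kaplan-Meier estimates at Month 10. Every retained patient passes Month 10 by study end (minimum 13 months). If the table is produced at the primary analysis, the last patients have only about 9 months and the Kaplan-Meier form is the safer choice.
- Keep entire-study tables by IFU version as descriptive only, show follow-up time for each subgroup, and note that they are not comparable across the two periods.
- Do not make whole-study events per patient-year the comparison, because it biases front-loaded events against IFU 10.
- Leave unchanged the existing rule that keeps PDS-related ocular events after explant whenever they start; a blanket cut at 90 days after explant would drop them.

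The cost is SAP wording and one extra table. Events after Month 10 would no longer enter the comparison between IFU versions, though they would still be reported.
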